A safety committee will be set up to handle all reports of adverse and suspected adverse events (AEs) and serious adverse events (SAEs). MBJ will head the committee.

Introduction

6 Background and rationale

In 2023/2024 the POCUS IN PRACTICE (PIP) study, a large stepped wedged cluster randomized clinical trial (SW-CRT) will be conducted in general practice in Denmark. The overarching aim of this study is to evaluate the implementation of point-of-care ultrasound (POCUS) in Danish general practice. An educational intervention for this study has been developed and tested in a previous study (Evaluating scanning competence following a structured POCUS training program for general practitioners: A hybrid effectiveness-implementation study: Clinical trials registration: NCT05274581). Since then, the intervention has been further developed and in line with the medical research council's framework for developing and evaluating complex interventions², the intervention is ready for the next stage of evaluation (figure 1).

Figure 1. Flowchart of the study process

OK 22: Projects included in the 2022 collective agreement between Danish Regions and The Danish Association of General Practitioners.
OK 25: The 2025 collective agreement between Danish Regions and The Danish Association of General Practitioners, will possibly include a larger scale implementation of POCUS in general practice depending on the results of the OK22 projects.

7 Specific objectives

Being a hybrid type 2 effectiveness-implementation study³, this study aims to simultaneous assess the clinical effectiveness of the intervention and to measure the impact of the implementation strategy as co-primary aims. The implementation-related outcomes have been developed based on recommendations for implementation strategy measures for use in feasibility and pilot implementation studies⁴.

Outcomes to assess the effectiveness of the intervention:

For GPs attending a 3-months basic POCUS course, we aim to determine:

(E1) how the frequency of use of different POCUS examinations develops in the first two years after introducing POCUS use in general practice including the variation over time and between GPs.

- (E2) how the frequency of referrals for secondary care develops in the first two years after introducing POCUS use in general practice and including the variation in referrals over time and between GPs.

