- (E3) how the number of consultations delivered in primary care develops in the first two years after introducing POCUS use in general practice including the variation over time and between GPs.
- (E4) how the GPs' reported effect of POCUS on their clinical decision and patient management in general practice develops in the first year after introducing POCUS use in general practice.
- (E5) the number of unwanted cases associated with the use of POCUS reported by the participating GPs in the first two years after introducing POCUS use in general practice.

Outcomes to assess implementation strategy effects:

- (I1) Adoption: the proportion of participating GPs that adopt the intervention and start using POCUS in their daily practice during the educational interventions (months 1-3).
- (I2) Fidelity (adherence): the proportion of participating GPs that complete the educational elements in the intervention (pre-post tests, webinars, assignments, attendance on seminar days, logbook registrations).
- (I3) Reach (penetration): The proportion of teachers who actively support participants by engaging in the online part of the educational interventions
- (I4) Sustainability (maintenance): the proportion of participating GPs that adopt the intervention and continue to use POCUS in their daily practice following the educational interventions (months 5-6).

Outcomes to inform further development of the implementation strategy

- (D1) Adaptability: the extent to which the teachers and participants find that the implementation of the educational intervention meets local needs
- (D2) Acceptability: the extent to which the teachers and participants find the implementation of the educational interventions is agreeable in terms of content and delivery
- (D3) Feasibility: the extent to which the teachers and participants find the educational intervention to be suitable for implementation
- (D4) Compatibility (appropriateness): the extent to which the teachers and participants perceive the implementation of the educational intervention is in line with the organisation's values, mission, priorities
- (D5) Dose (satisfaction): the extent to which the teachers and participants are satisfied with the amount of support and resources received as part of implementation strategy
- (D6) Complexity: the extent to which the teachers and participants perceive the implementation of the educational intervention as being difficult or complex

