Outcomes to assess the effectiveness of the intervention:

Following the use of POCUS in the general practice consultations the GPs will follow normal procedures for registration of activities in general practice using remuneration codes, fee-specific codes for using POCUS, and referrals in the medical record system. Prior to this study 11 fee-specific codes for 11 different POCUS examinations will be installed in the medical record system. The Primary Sector Data Provider Platform (PLSP) will develop an algorithm that allows for the following data extraction on each participating GP in a given time frame: (1) number of POCUS examinations performed, (2) number of referrals, and (3) number of consultations (outcomes E1-3). PLSP will deliver monthly aggregated data for each participating GP from baseline to 24 months after baseline. These continues data will be summarized to demonstrate variation over time.

For the registration of the clinical effect of POCUS use in the consultation (outcome E4), we will use an adapted version of a questionnaire used in a previous cohort study²⁴. The GPs will be asked to specify the following for each POCUS examination: (1) organs/structures examined with POCUS (drop down menu or free text), (2) whether POCUS use entailed a change in diagnosis (yes/no), (3) whether POCUS use entailed a change in referral (yes/no), (4) whether POCUS use entailed a change in treatment (yes/no), (5) whether POCUS use entailed a change in diagnostic certainty for the GP (yes/no), (6) whether POCUS use was helpful for the GP in terms of making a decision for patient management (5-point Likert scale), (7) whether POCUS use was helpful for the GP in terms of arriving at a diagnosis (5-point Likert scale). GP will assess the questionnaire immediately after performing POCUS during consultations in clinical practice. These categorical data will be collected for each participating GP from day 7 to day 372.

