The data management will follow the rules of the General Data Protection Regulation (GDPR) and the Danish Data Protection Agency. All study data will be stored on a secure server at Aalborg University. Questionnaire data will be collected using the online platform SurveyXact (Rambøll, Aarhus, Denmark). A data management agreement has been made between Rambøll and Aalborg University. At the end of the data collection, data will be moved from SurveyXact to Aalborg University's server.

Register data will be collected by PLSP. Data management agreements between PLSP and CAM AAU will be made prior to the collection of data. PLSP will receive data from the different IT suppliers for the general practice clinics. Data management agreements between the IT suppliers and PLSP as well as the GP clinics and the IT suppliers already exists. For this specific study, we will develop an instruction for the GPs to incorporate in the existing data management agreement prior to the collection of data.

All patient-related data will remain in the GPs clinics until the end of the educational intervention (day 97). No data will be transferred to CAM AAU before legal approval by the health authorities has been obtained.

20a Statistical methods for analysing primary and secondary outcomes.

All statistical analyses will be performed using STATA version 17 (StataCorp, Texas, USA) and analyzed according to a predefined statistical analysis plan, which will be uploaded to clinical Trials.org prior to the analysis of data (24 months after baseline). Data will be summarized and reported using descriptive statistics.

For effectiveness related outcomes E1-E5, frequencies and variance are reported as mean and 95% CI or median and IQR depending on the distribution of data. We will use graphic illustrations to demonstrate change over time. To test if changes over time are significant, we will use repeated measures ANOVA analysis.

For outcomes related to the implementation strategy effects (I1-I4) and feasibility of trial methods (F1-F7), we will report proportions as frequencies, while outcomes related to the implementation strategy (D1-D9) will be reported with an average score and outcomes D10-D11 with a summarized estimate on costs. For feasibility related outcome F8, we will report the questionnaire response rate and the corresponding 95% CI.

20b Methods for any additional analyses (e.g. subgroup and adjusted analyses).

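### POCUS use (E1) and referrals (E2) are tested over time as monthly numbers per GP with no adjustment for work volume, so holiday months and leave can appear as change in behaviour

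*Protocol*

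**What the plan says.** Section 7 of the protocol sets three related objectives: E1, "how the frequency of use of different POCUS examinations develops in the first two years after introducing POCUS use in general practice"; E2, "how the frequency of referrals for secondary care develops in the first two years"; and E3, "how the number of consultations delivered in primary care develops in the first two years". Each also asks about variation over time and between GPs. The first two speak of frequency and the third of a number. None names a denominator.

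Section 12 defines what is measured for each GP: "1) number of POCUS examinations performed, (2) number of referrals, and (3) number of consultations (outcomes E1-3". The unit is the GP-month: "PLSP will deliver monthly aggregated data for each participating GP from baseline to 24 months after baseline". The workload descriptors among the participant characteristics are the practice's list size and its number of GPs, taken once on day 7. Working hours, part-time status and leave are not listed.

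Section 20a treats the effectiveness outcomes alike: "For effectiveness related outcomes E1-E5, frequencies and variance are reported as mean and 95% CI or median and IQR", depending on distribution, with graphs of the course over time and repeated measures ANOVA as the test of change. It mentions no rate, offset, working-day adjustment or calendar term. It also says that the analysis will follow a predefined SAP.

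**The concern.** A monthly number of scans or referrals is the product of how many patients the GP saw and how often the GP scanned or referred per patient seen. Only the second factor is clinical behaviour. If the number is tested without the first factor, a month with fewer working days counts as change.

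Nothing else in the design absorbs this. There is no comparison group (sections 16a and 16b do not apply). The first seminars are on 31 August and 6 September 2022 (section 13), so every GP meets each holiday period at nearly the same time since training. Register data run from the first seminar (section 18a), so no earlier year shows the usual seasonal pattern.

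Clinical effectiveness is one of the two co-primary aims. A statistically significant change in referrals that only traces the holiday calendar could be reported as a development after POCUS was introduced.

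**Working it through.** **1. When the holidays fall.** With September 2022 as month 1, December is months 4 and 16 and July is months 11 and 23, for both courses. The third seminars are on 29 and 30 November 2022, so the first full month after the course is a December.

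**2. Inputs.** The protocol gives 21 expected GPs, one scan a day and 24 months (sections 12 and 14). Section 14 equates 24 months with 200 working days, but 21 × 1 × 200 = 4,200, whereas its 8,400 registrations need 21 × 1 × 400. The check therefore takes 200 working days per year. That discrepancy is a separate matter. Everything else is assumed, because the documents do not give it: 20 consultations a day, 1 scan per 20 consultations on average, 6 referrals per 100 consultations, the seasonal patterns and a significance level of 0.05.

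**3. One holiday month.** Expected count = working days × consultations per day × rate per consultation. In the mild pattern (July 25%, October 10% and December 15% below other months, scaled to 200 days a year), the monthly weights sum to 9 + 0.75 + 0.90 + 0.85 = 11.5. An ordinary month then has 200 / 11.5 = 17.4 days, and July has 0.75 × 17.4 = 13.0.

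- Ordinary month: 17.4 × 20 = 348 consultations, 348 / 20 = 17.4 scans, 348 × 0.06 = 20.9 referrals.
- July: 13.0 × 20 = 260 consultations, 260 / 20 = 13.0 scans, 260 × 0.06 = 15.6 referrals.

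Both counts fall by about 25%. The rates stay at 5 scans and 6 referrals per 100 consultations.

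**4. The planned test.** 1,000 studies of 21 GPs over 24 months were simulated. Work volume and scan rate varied between GPs, working days varied at random by GP-month, and the rates per consultation were constant over time. The stronger pattern has July, October and December in the ratio 12, 17 and 15 days against 20–21 in other months. The table gives the share of studies with p < 0.05 after Greenhouse-Geisser correction; figures in brackets are uncorrected and were computed for scans only.

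| Assumed season | Scans, count | Scans, per consultation | Referrals, count | Referrals, per consultation |
|---|---|---|---|---|
| None | 0.6% (6.3%) | 0.5% (5.0%) | 0.4% | 0.9% |
| Mild | 96.0% (99.8%) | 0.2% (4.1%) | 99.4% | 1.3% |
| Stronger | 100% (100%) | 0.8% (4.3%) | 100% | 0.7% |

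The corrected test is conservative with 21 GPs and 24 time points, and it still signals change on the counts almost every time.

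**5. Leave.** A GP of average volume who is away for a month shows a fall to zero in the individual series and lowers the group mean by 1/21 = 4.8%. Unless leave coincides, it affects the individual curves more than the group test.

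**6. Part-time work.** A GP with half of the 348 consultations has 174, hence 8.7 scans against 17.4, at the same 5 per 100. The difference is the same every month, so it widens the spread between GPs. Repeated measures ANOVA removes the constant part from the test of time.

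**The case against.** The strongest reply is that section 12 only lists what the register extract contains, and that section 20a refers the analysis to a SAP that is not at hand. Denominators and zero-consultation months are ordinary SAP detail, the word frequency does not exclude a rate, and every input for a rate is collected. This stands in part: the SAP may define a rate and so settle the matter. But the protocol itself states the measure as a number and names the test. The point concerns that stated combination.

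Second, E3 will be shown for the same GPs and months, and 24 months cover each calendar month about twice, so a careful reader could see all three series dip together. That helps with the graphs. It does not alter a significance test on the counts.

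Third, total scans and referrals per GP are meaningful measures of service use. That stands, and it is why the count should be kept.

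A reader might infer more than the documents support:

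- **That part-time work appears as change over time.** Constant part-time work does not; only a change in working time does.
- **That a GP on leave would be classed as having stopped scanning.** No rule for E1 or E2 does this. Continued use is the separate outcome I4.
- **That the rate should replace the count.** Consultations are themselves outcome E3 and may move with POCUS use, in which case the rate shifts although the numbers of scans and referrals do not.
- **That the simulated percentages predict this study.** They follow from assumed seasons with constant rates built in.

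**Conclusion.** The concern holds in this form. As written, the plan tests monthly numbers per GP for change over time without regard to work volume, in a single-group study where calendar month and time since training nearly coincide. Common holiday months can therefore produce a significant change in POCUS use or referral with behaviour unchanged. Leave does the same in an individual GP's series, and stable differences in working time inflate the described variation between GPs.

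The direction follows from the definition of a count. The size depends on the seasonal pattern, which the documents do not give: under the two assumed patterns the test on counts signalled change in 96–100% of simulated studies, against about 1% or fewer per consultation, both after correction. With no season, the count behaves properly. The conclusion does not make the count a wrong measure; used alone, it cannot support a claim about scanning or referral behaviour.

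**What to change.** In sections 12 and 20a, and in the SAP to match:

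- For each GP-month, report and test E1 and E2 also as rates per 100 consultations, or with a count model that has log consultations as offset, alongside the raw counts.
- In the rate analysis, treat GP-months with zero consultations as not at risk, not as zero use.
- Keep E3 as a count.
- Base any claim of changed scanning or referral behaviour on the rate read together with the count and E3, because consultations may themselves change with POCUS.

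The cost is a change of wording and one more set of results, since consultations for the same GP and month are already in the register delivery. The rate removes differences in work volume only; a seasonal shift in the kinds of patients seen would remain and should be acknowledged when the curves are interpreted.

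### E4 records change in referral, diagnostic certainty and treatment without direction, so neither the proportion of yes answers nor its first-year trend shows which way practice moved

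*Protocol*

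**What the plan says.** Section 7 lists E4 among the effectiveness outcomes. Its objective is "how the GPs' reported effect of POCUS on their clinical decision and patient management in general practice develops in the first year".

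Section 12 sets out seven items that the GP completes for every POCUS examination. After the organ scanned come four yes/no items. They concern diagnosis, referral ("whether POCUS use entailed a change in referral (yes/no"), treatment ("whether POCUS use entailed a change in treatment (yes/no") and certainty ("whether POCUS use entailed a change in diagnostic certainty for the GP (yes/no"). The last two items are ratings: "whether POCUS use was helpful for the GP in terms of making a decision for patient management (5-point Likert scale" and "whether POCUS use was helpful for the GP in terms of arriving at a diagnosis (5-point Likert scale". Collection runs from day 7 to day 372. Section 18a specifies paper logbooks up to day 96 and an online form from day 97.

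Section 20a summarises E1 to E5 descriptively and tests change over time by repeated measures ANOVA. Referrals also form a separate outcome, E2, on "how the frequency of referrals for secondary care develops in the first two years". Its data are monthly totals per GP.

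**The concern.** Certainty can rise or fall, and a referral can be added, averted or redirected. The items record only that something changed. E4 is the only measure of clinical effect taken at the level of the single scan, so a direction that it does not capture is not available elsewhere.

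Two things are at stake. First, the proportion of yes answers measures how often scanning altered something, but not in which direction. Second, the objective concerns development over the first year among GPs who are learning the technique. The mix of directions could shift as skill grows while the proportion of yes answers stays flat, or the proportion could move for either of two opposite reasons. For the same reason, E4 could not help to explain a movement in E2.

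**Working it through.** The protocol states no figure on this point, so there is none to reproduce. The check has four parts.

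**1. What each E4 item captures (section 12)**

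| Item | Subject | Answer | Direction recorded? |
|---|---|---|---|
| 2 | Diagnosis | yes/no | No natural direction |
| 3 | Referral | yes/no | No |
| 4 | Treatment | yes/no | No |
| 5 | Diagnostic certainty | yes/no | No |
| 6 | Helpfulness for management | 5-point scale | No: an added and an averted referral can both be helpful |
| 7 | Helpfulness for diagnosis | 5-point scale | No: at most an indirect hint for item 5 |

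**2. Whether another source supplies the direction**

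- E2 gives monthly totals per GP. It shows the overall trend in referrals but is not linked to individual scans.
- E5 is reported as monthly counts of unwanted cases. Its free text goes to the safety committee and is not reported. It does not concern whether a referral was added or certainty fell.

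**3. What a given proportion of yes answers allows**

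Let x be the share of scans answered yes for referral. Among these, let a be the share averted, d added and r redirected, with a + d + r = 1.

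Net change in referrals per 100 scans = 100 · x · (d − a).

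E4 records x whatever a, d and r are. The possible range is ±100 · x · (1 − r).

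The protocol gives no value for x or r, so both are assumed here:

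| x | r = 0 | r = 0.5 |
|---|---|---|
| 10% | −10 to +10 | −5 to +5 |
| 30% | −30 to +30 | −15 to +15 |
| 50% | −50 to +50 | −25 to +25 |

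With x = 30% and r = 0, averted shares of 0, 0.25, 0.5, 0.75 and 1 give +30, +15, 0, −15 and −30 per 100 scans. The recorded result is 30% in all five cases.

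The same reasoning applies to the trend in certainty. Let u be the share of changes that are increases, so that net change per 100 scans = 100 · x · (2u − 1). Assume x = 40% in both month 1 and month 12, with u = 0.5 first and u = 1 later. The net moves from 100 · 0.40 · 0 = 0 to 100 · 0.40 · 1 = +40. E4 shows 40% at both times, which reads as no development.

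**4. Whether the form can still be changed**

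The first seminar is day 7 and took place on August 31st 2022 (course 1) and September 6th 2022 (course 2), by section 13. Day 372 is 372 − 7 = 365 days later: August 31st and September 6th 2023. Section 25 says in the past tense that register data became available only in November 2024. The version line in section 3 is dated August 2022, but the amended text was evidently written after the E4 window had closed.

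**The case against.** The strongest reply is that the E4 objective is neutral. It asks about a reported effect on decisions and management, and an any-change proportion answers that as written. A reader might go further than the text and infer that a high proportion of yes answers is put forward as benefit, or that it conceals net harm. The documents support neither. Nowhere does the protocol equate a yes with better certainty or fewer referrals, or say that E4 will explain E2. An added referral or lower certainty may be the right outcome of a scan. Harm has its own channels in E5 and in the adverse event reporting of section 22. This part of the reply stands: the point is a limit on interpretation, not a contradiction.

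Other replies stand in part:

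- Item 7 can be cross-tabulated with item 5 for the same scan, since a scan that lowered certainty is perhaps less likely to be rated helpful for diagnosis. That is partial information on certainty and none on referral.
- For treatment, neither starting nor stopping is inherently better, so the case for direction is weaker than for items 3 and 5.
- The questionnaire is an adaptation of an earlier one and is not reproduced. Follow-up fields cannot be excluded, although the listed formats suggest none.
- Short binary items are a defensible choice for a form completed immediately after each scan, when section 16c looks for 90% obtainable and valid questionnaire data (F7).
- A change of answer format partway through would disturb the trend unless the new categories can be collapsed to the old ones.

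**Conclusion.** The point holds as a weakness of measurement that is worth correcting. As specified, items 3 and 5, and to a lesser degree item 4, cannot show whether certainty rose or fell, whether referrals were added, averted or redirected, or whether that mix changed over the year. The loss occurs when the form is completed, so it cannot be left to the statistical analysis plan.

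The size can be stated only as a range. A proportion x of yes answers for referral fits any net effect within ±100 · x · (1 − r) per 100 scans. The rates used above are assumptions. What does not depend on them is that the sign is not identified. The conclusion assumes that the form contains no directional fields beyond those listed in section 12. It does not extend to a claim that POCUS use caused net harm or that the protocol presents a yes as improvement.

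**What to change.** In both the paper logbook and the online form, replace the yes/no answers by:

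- **Certainty:** increased / unchanged / decreased.
- **Referral:** averted / no change / added / redirected.
- **Treatment:** started or intensified / no change / withheld or stopped / other.

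Report each category, and beside it the collapsed any-change proportion, so that the series stays comparable with yes/no registrations. If the form already has directional follow-up fields, state them in section 12.

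For registrations already collected as yes/no, which on the dates above is probably all of them, report any change only. Do not describe them as improved certainty or fewer referrals, and do not use them to explain E2. Apply the directional lists in any remaining collection and before the form is reused in the planned stepped-wedge trial.

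The reporting limit costs only wording. The new lists mean editing three answer sets in two formats and a slightly greater burden per scan, which should be watched against the F7 completeness criterion. They cannot recover direction for past scans.

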For the registration of unwanted cases (outcome E5), we will use a questionnaire giving the GPs the possibility to explain in free text using their own words to explain (1) what was scanned, (2) circumstances surrounding the scan, (3) what happened, and (4) reflections after the scan. Data will be collected from baseline to 24 months after baseline. We will report the aggregated total number of monthly registrations for each participating GP. The free text elaborations will not be reported, but passed on to the safety committee (see section 5d). The assessment of unwanted cases for the study does not substitute the GP's registration of untoward incidents required by Danish law (<https://stps.dk/da/ansvar-og-retningslinjer/vejledning/rapporteringspligt/>).

Outcomes to assess implementation strategy effects:

For the assessment of implementation strategy effects (outcomes I1-4), we will use the register data (fee specific codes) collected by PLSP on the monthly use of POCUS for each participating GP (outcomes I1 and I4) and the activities logged (pre-post tests, webinars, assignments, attendance on seminar days, logbook registrations) in the online platform used in the educational intervention (outcomes I2-3) to estimate the frequency of use and the percentage of adherence, respectively. The continues data (outcomes I1 and I4) will be collected prospectively from day 7 to day 372, while the binary data (outcomes I2 and I3) are collected retrospectively at the end of the educational intervention including registration made in the online platform from day 1 to day 97 (at the end of the educational intervention).

Outcomes to inform further development of the implementation strategy

For outcomes related to the development of the implementation strategy (outcomes D1-D11), we will use a questionnaire distributed to participants three months after introducing POCUS in

general practice and teachers following the final teaching seminar (day 97). A reminder will follow after 2 weeks. The questionnaire will include the following questions with a 5-point Likert scale:

- (D1) Did the educational intervention meets local needs?
- (D2) Was the educational interventions agreeable in terms of content and delivery?
- (D3) Was the educational intervention suitable for implementation?
- (D4) Was the educational intervention in line with your values, mission, priorities?
- (D5) Are you satisfied with the amount of support and resources allocated to you?

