We will perform subgroup analysis to explore the effects of participants' background characteristics and type of POCUS examinations performed. This will be elaborated in the SAP.

20c Missing data

Missing values, owing to e.g. premature termination of the questionnaire, are considered completely random and will be declared for each outcome. A sensitivity analysis will be performed in cases, where missing values are not considered random.

Data monitoring

21a Data monitoring committee (DMC).

The principal investigator (CAA) will monitor the data collection and contact the project steering committee in case of problems related to data collection or the validity of the collected data. The principal investigator (CAA) will also contact the steering committee in care of participant drop-out.

21b Description of any interim analyses and stopping guidelines, including who will have access to these interim results and make the final decision to terminate the trial

n/a

22 Harms

The participating GPs will be obliged to report any undesirable effects including Suspected Unexpected Serious Adverse Reactions (SUSARs), Serious Adverse Events (SAEs) and Adverse Events (AEs) related or possibly related to the use of POCUS to the safety committee.

23 Auditing

n/a

Ethics and dissemination

24 Research ethics approval

The study will be performed in accordance with the Declaration of Helsinki. The project was notified to The North Denmark Region Committee on Health Research Ethics.

(Den Videnskabsetiske Komité for Region Nordjylland, reference number 2022-000764) who responded that according to Danish Law (komitélovens § 14, stk. 2), no ethical approval is needed for this project.

As we are collecting patient-related data for the purpose of research, we will seek permission by the health authorities (Application sent October 13th 2022). All patient-related data will be collected retrospectively after this approval is obtained. We will honor our information obligations to patients about the project by making project information available in the GP's clinic as hand-outs and posters.

The project has been registered and conducted according to the regulations of the Danish Data Protection Agency (registration number ID 242-3).

25 Protocol amendments

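### E5 is summarised and trend-tested as a raw count of reported unwanted cases, so it moves with scan volume and gives no result by seriousness

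*Protocol*

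**What the plan says.** Section 7 defines E5 as "the number of unwanted cases associated with the use of POCUS reported by the participating GPs" over the first two years. Section 12 describes a form with four free-text items and no field for seriousness, and then fixes the result: "We will report the aggregated total number of monthly registrations for each participating GP". On the content it says: "The free text elaborations will not be reported, but passed on to the safety committee".

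Section 20a sets the analysis: "For effectiveness related outcomes E1-E5, frequencies and variance are reported as mean and 95% CI or median and IQR", depending on the distribution. The same paragraph plans a repeated measures ANOVA for change over time. It mentions no rate and no exposure term.

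For scan numbers (E1), section 12 says: "PLSP will deliver monthly aggregated data for each participating GP from baseline to 24 months after baseline". Section 18a gives the same window, day 7 to day 829, for the E1 register data and the E5 reports. It also describes the reporting of unwanted cases as anonymous.

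Section 22 obliges GPs to report SUSARs, SAEs and AEs that may be related to POCUS to the safety committee. Section 5 gives that committee the handling of AE and SAE reports.

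**The concern.** E5 is the only harm outcome among E1 to E5, in a study that feeds a larger trial and possibly wider use of POCUS. The number of scans is the very quantity that E1 expects to vary over time and between GPs. Participants are first encouraged to scan as much as possible, then to scan all suitable patients, and only some may receive a fee per scan. A count of reported cases will tend to follow that variation. A significant rise or fall in raw E5 could then be read as a change in safety when only use has changed, and a real change in risk could be hidden.

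A single total also gives a serious event and a trivial one the same weight. The categories in section 22 could separate them, but they are not carried into any planned result.

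**Working it through.** **1. The plan's exposure figure.** Section 14 gives 21 GPs, one scan per day, 200 working days for the 24 months, and 8,400 expected registrations.
- As stated: 21 × 1 × 200 = 4,200. This does not reproduce 8,400.
- With 200 working days in each of two years: 21 × 1 × 400 = 8,400. This does.

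Both totals are carried below as a range.

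**2. How the count responds to use.** Expected monthly E5 over all GPs = GPs × scans per GP-month × reported cases per scan. The protocol gives no event rate and no monthly scan pattern, so the risks and the 10 and 20 scans per GP-month are assumptions. Reporting behaviour is held constant.

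| Scenario | Calculation | Cases per month | Cases per 1,000 scans |
|---|---|---|---|
| 10 scans, risk 0.5% | 21 × 10 × 0.005 | 1.05 | 5 |
| 20 scans, risk 0.5% | 21 × 20 × 0.005 | 2.10 | 5 |
| 10 scans, risk 1% | 21 × 10 × 0.01 | 2.10 | 10 |
| 20 scans, risk 0.5% | 21 × 20 × 0.005 | 2.10 | 5 |

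Rows 1 and 2: use doubles at constant risk, the count doubles and the rate is unchanged. Read backwards, halved use halves the count. Rows 3 and 4: risk halves while use doubles, the count is unchanged and the rate halves. The count and the rate answer different questions, and only the count is planned.

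**3. How sparse the GP-month counts may be.** At 8,400 scans the average is 8,400 / (21 × 24) = 16.7 scans per GP-month. For an assumed risk of 0.1% to 1%:
- total cases: 8.4 to 84 (4.2 to 42 at 4,200 scans);
- cases per GP-month at 8,400 scans: 0.017 to 0.167;
- chance that a GP-month shows zero, (1 − risk)^16.7: about 98% down to 85%.

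Monthly figures for single GPs would be mostly zeros, so a pooled rate is the more informative summary.

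**4. What zero reports would mean.** The exact Poisson two-sided 95% upper limit for 0 events is −ln(0.025) = 3.689.
- 3.689 / 8,400 = 0.44 per 1,000 scans.
- 3.689 / 4,200 = 0.88 per 1,000 scans.

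A mean or median count of zero conveys neither figure.

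**5. Seriousness.** Section 22 distinguishes SUSARs, SAEs and AEs. The E5 form in section 12 has no such field, and the E5 result is one total. No section says that the committee's view of a report will be tabulated, or whether reports under section 22 are counted in E5.

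**6. Anonymous or by GP.** Section 12 promises counts for each GP, while section 18a calls the reports anonymous. If they carry no GP identifier, neither counts nor rates per GP can be formed, and only pooled figures are possible.

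**The case against.** The count matches the stated objective, which asks for a number of cases and not a risk per scan, and the study is small and preparatory. This is a fair reason to keep the count. It does not justify testing raw counts for a trend, because that result invites a reading about safety which it cannot support.

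Four stronger readings are tempting, and the documents do not support them.
- *That E5 will appear without any scan numbers.* Section 31a puts the effectiveness outcomes in one article, so E1 will stand beside E5 and a reader could form a crude ratio. What is missing is the link in the planned E5 summary and test.
- *That seriousness is ignored.* The free text and the AE and SAE reports go to a safety committee. Only a planned result by seriousness is absent.
- *That E5 could be zero while the committee holds SAE reports.* This rests on silence about the route for section 22 reports. The only GP reporting tool described is the E5 form, and its content goes to the same committee. Part of section 5 was not available to this review, so the silence is weak evidence.
- *That the zero-event limit bounds true harm.* E5 counts what GPs choose to report. The limit also treats events as independent, although they are clustered within about 21 GPs.

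It can also be said that the statistical analysis plan may add a rate or a table of classes. It may, and that makes the change easy. But the reporting rule and the trend test are set in the protocol itself.

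**Conclusion.** The point holds in this form: E5 as fixed is a raw monthly count put through a test of change over time, with no exposure term and no result by seriousness. The summary and the test move with scan volume and cannot show whether reported harm per scan changes.

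The size follows from proportionality: a doubling or halving of use carries straight through to E5. This assumes constant risk and constant reporting behaviour. Changes in reporting would also move the count, and a rate would not cure that. The risks used in the illustrations are assumed, because the protocol gives none. The limits of 0.44 and 0.88 per 1,000 are exact for the two scan totals but apply to reported cases only.

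The conflict between anonymous reports and counts by GP stands on its own and must be settled before any E5 analysis by GP.

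**What to change.** - **Rate.** Keep the count, but report E5 mainly as reported unwanted cases per 1,000 coded POCUS examinations, using the monthly E1 data. Give an exact Poisson 95% CI for the pooled rate, or an interval that allows for clustering by GP if reports can be linked to GPs.
- **Trend.** Do not interpret a test of raw E5 counts as a safety trend.
- **Seriousness.** Have the existing safety committee class each report as serious or non-serious, and tabulate the classes without the free text.
- **Routes.** State whether section 22 reports enter E5, and count each event once.
- **Anonymity.** Reconcile sections 12 and 18a. If reports are anonymous, give only pooled monthly rates.

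The cost is wording in the analysis plan, a matching correction to the protocol, and a short classification task for the committee. No new exposure data are needed. The downside is an imperfect denominator: scans on volunteers and uncoded scans are missing from it, and under-reporting remains. Both should be stated with the result.
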